PROTOCOL TITLE:

Naloxone Auto-injector as a Universal Precaution for Patients with Opioid Substance Use Disorder (DSM-V)

PRINCIPAL INVESTIGATOR:

Name: [name]. Department: Neurosurgery

VERSION NUMBER:

Version 5.0

DATE:

9/11/2018

REGULATORY FRAMEWORK:

Please indicate all that apply:

DOD (Department of Defense)
DOE (Department of Energy)
DOJ (Department of Justice)
ED (Department of Education)
EPA (Environmental Protection Agency)
FDA (Food and Drug Administration)
HHS (Department of Health and Human Services)
Other:

If yes, please confirm that the research team is familiar with and agrees to comply with the investigator requirements cited in ICH-GCP E6. Yes No ICH-GCP E6 can be accessed by copying and pasting this URL into your browser: http://www.fda.gov/downloads/Drugs/Guidances/ucm073122.pdf

Table of Contents

1.	Objectives	3
2.	Background	3
3.	Study Design	8
4.	Inclusion and Exclusion Criteria	8
5.	Number of Subjects	8
6.	Study Timelines	9
7.	Study Endpoints	9
8.	Research Setting	9
9.	Resources Available	
10.	Prior Approvals	
11.	Multi-Site Research	14
12.	Study Procedures	14
13.	Data Analysis	15
14.	Provisions to Monitor the Data to Ensure the Safety of Subjects	16
15.	Withdrawal of Subjects	16
16.	Data Management/Confidentiality	17
17.	Data and Specimen Banking	19
18.	Risks to Subjects	19
19.	Potential Benefits to Subjects	
20.	Recruitment Methods	
21.	Provisions to Protect the Privacy Interests of Subjects	
22.	Economic Burden to Subjects	
23.	Compensation	
24.	Compensation for Research-Related Injury	
25.	Consent Process	
26.	Documentation of Consent	
27.	Study Test Results/Incidental Findings	
28.	Sharing Study Progress or Results with Subjects	
29.	Inclusion of Vulnerable Populations	
30.	Community-Based Participatory Research	
31.	Research Involving American Indian/Native Populations	
32.	Transnational Research	
33.	Drugs or Devices	
Che	cklist Section	

1. Objectives

To conduct a pilot study of a naloxone auto-injector in a "Universal Precaution" manner for patients with opioid substance use disorder. Our three objectives are:

- 1) To decrease the number of fatal and nonfatal overdose deaths by use of the naloxone auto-injector by co-prescribing in the University of New Mexico Addiction and Substance Abuse Program (UNM ASAP).
- 2) To study the characteristics of the study subjects who performed the overdose reversals (vs. the study subjects who did not) using a biostatistical logistic regression analysis
- 3) To qualitatively study the in-depth characteristics of study subjects who a) documented many overdosed reversals/"saved" many community members, b) documented one overdose reversal/"saved" one community member, and c) did not document any overdose reversals.
- 4) Study the 2 mg Evzio autoinjector product to prospectively analyze the difference in doses (2 mg vs. 0.4 mg) needed to reverse an overdose. The goal will be to recruit 100 patients in one year and document between 20-30 overdose reversals in the community.

Note: Between April 4th 2016 and April 4th 2017, 383 study subjects were enrolled and there were 93 reported overdose reversals. We are currently enrolling new patients at the rate of 6-10 new patients per month.

2. Background

a. The use of naloxone auto-injectors to block the pharmacological effects of opioid medications may have a positive impact on the overdose deaths from prescription opiates if utilized in a manner similar to other emergency devices. Several formulations are available including intravenous, intramuscular, and subcutaneous injections, all of which are commonly used administration routes. Adverse events due to opioid overdose can occur in many situations, and risk of death increases if treatment is not administered immediately. Because of respiratory depression, there is not enough time for patient transport to the emergency room before treatment is initiated. The risk of death, and/or cerebral hypoxia/anoxia increases substantially. A formulation of naloxone that is easy to administer under any condition could be utilized as a "rescue kit" in the same conceptual manner of "Universal Precautions" as a glucagon injection is used for a person that uses insulin to control blood sugar in an emergency.

According to the National Survey on Drug Use and Health, between 55% of patients dying of an unintentional opioid overdose obtain their medication from a friend or relative.¹ 17.3% of patients dying of an unintentional opioid overdose obtain their medication directly from one doctor. Additionally, unintentional opioid overdoses remain the third leading cause of childhood poisonings at 7.9% of all childhood poisonings (after cosmetics and cleaning products).²

b. Drug Prescription Overdose Death in the United States and New Mexico

Death due to opioid overdose is a serious issue in the Unites States. The Center for Disease Control reports that 14,800 people in the United States died of prescription opioid overdose in 2008, more than triple the figure from 1999.⁵ Additionally, 475,000

emergency room visits due to misuse and abuse of prescription opioid were reported in 2009.⁵

Opioid use and related deaths are critical issues in New Mexico. In 2008, New Mexico had the highest opioid overdose death rate in the Unites States --27.0 deaths per 100,000 population, 2.3 times higher than the U.S. average of 11.9 in 2008.^{5,6} Although the death rate was reduced to 21.6 deaths per 100,000 population in 2009, it rose to 23.3 deaths in 2010 and 25.9 deaths in 2011. Both figures still exceed the U.S. average.⁷ Moreover, not only is the opioid death rate high in New Mexico, the overdose death rate for the illicit drug heroin is also high. Although the rate per 100,000 population of opioid overdose deaths was the worst in 2010 in New Mexico, the rate of prescription painkillers sold was 6.7 per 100,000 population, which was not the highest opioid sales rate in the United States (highest: Florida, 12.6 per 100,000 population; the US average: 7.3 per 100,000 population).⁵ A confounder to this issue is that at this time the national mortality data provided by the Centers for Disease Control and the mortality data for New Mexico provided by the Office of the Medical Investigator are not able to define if deaths are due to illicit opiate use such as heroin, prescribed opiate use or both. This indicates that drug overdose deaths may be due to greater misuse of pain medications in New Mexico.

Furthermore according to the Office of Adolescent Health, 8% of adolescents (ages 12-17) in New Mexico used pain relievers, including opioids, for nonmedical purposes whereas the U.S. average was 6% in 2011.⁸ The rate of exposures to tobacco, alcohol, and other illicit drugs was also higher in New Mexico than the U.S. average.⁸ The availability and use of drugs at an early age may contribute to the reasons why New Mexico has one of the highest rates of drug over dose death in the nation.

Although drug overdose death rates varied by county in New Mexico, figures from the New Mexico Department of Health (NMDOH) show that the age-adjusted drug overdose death rate in New Mexico was 24.1 per 100,000, and illicit drug use and prescription drug use were equally contributed to the deaths.^{7,9} Bernalillo County, where the University of New Mexico Hospital study site is located, has the highest population in New Mexico (estimated 662,564 in April 2010), and approximately 30% of New Mexico's residents live in Bernalillo County.¹⁰ Bernalillo County experienced the 10th highest drug overdose death rate (25.4 per 100,000) in New Mexico between 2008 and 2012.⁷ This is greater than the U.S. average and the rate of New Mexico. Therefore, prevention of drug overdose deaths is a socially and epidemiologically critical issue in Bernalillo County, and any interventions for the prevention of drug overdose deaths must be established immediately.

c. Use of naloxone in the field to treat opioid overdose

• Treatment of Drug Overdose

The increase in deaths due to opioid overdose has contributed to the development of community-based overdose prevention programs, such as Project Lazarus, overdose education and naloxone distribution (OEND), and Project DAWN.¹¹⁻¹³ Naloxone is considered the primary antidote for opioid overdose and is vital in preventing fatal events. It is a competitive *mu* opioid-receptor antagonist that reverses opioid intoxication and is given via a parenteral, intranasal, or pulmonary route.¹⁴ Naloxone's onset of action is seen in less than two minutes and lasts 20 to 90 minutes.¹⁴ Dosing of naloxone is empirical, depending on many factors, including the quantity of opioid ingested, relative

affinity for the *mu* opioid-receptor, patient weight, and degree of penetration of the opioid into the central nervous system.¹⁴ Initially, a 0.04 mg dose of naloxone should be given intravenously for respiratory depression and other symptoms associated with opioid overdose.¹⁴ If the patient does not respond, the dose should be increased every two minutes to a maximum of 15 mg.¹⁴ For intramuscular or subcutaneous administration, a single dose of 0.4 mg is given, and it may repeat every 2 to 3 minutes until emergency medical assistance becomes available.¹⁴

• Project Lazarus¹¹

Wilkes County, which is in western North Carolina, had a population of approximately 66,500 in 2010. Their population was primarily composed of workers who historically suffered from chronic pain due to work-related injury. In 2009, the unintentional drug overdose death rate in Wilkes County was 46.6 per 100,000 population, or four times greater than the U.S. average. Thus, reducing unintentional drug overdose deaths was critical for Wilkes County.

The Wilkes County Health Department and the University of North Carolina took the initiative to launch a drug overdose prevention study. Its objectives:

• Establish a community-activated drug overdose prevention study and build a partnership among healthcare providers.

• Monitor data regarding unintentional drug overdose deaths before, during, and after the study.

- Prevent unintentional drug overdose deaths in the county.
- Use a naloxone rescue kit for people at risk of drug overdose deaths.
- Evaluate the project.

To accomplish these objectives, the research team educated primary-care physicians and people who were at risk of drug overdose death. The physicians received training to manage patients with chronic pain and to prescribe opioid safely with the naloxone rescue kits. The patients received education on pain management and opioids at a prescriber's office and received the naloxone rescue kit for free.

In 2010, the research team significantly reduced the number of unintentional drug overdose deaths to 29.0 per 100,000 population. Additionally, the number of drug overdose deaths due to prescription opioid was reduced to 10% (2010) from 82% (2008) of all drug overdose deaths in Wilkes County.

In only one year, the program was able to successfully reduce the number of unintentional drug overdose deaths in Wilkes County. The education for primary-care physicians and for high-risk patients of drug overdose deaths, along with the naloxone rescue kit, contributed to the dramatic changes.

• Overdose education and nasal naloxone distribution (OEND) program in Massachusetts¹²

The OEND program is also well-known clinical study that successfully decreased drug overdose deaths in Massachusetts. The Massachusetts Department of Public Health took the initiative for the study, the objective of which was to investigate the education of drug overdoses for people at high risk of drug overdose death and for bystanders (defined as "social service agency stuff, family and friends of opioid users"). The investigators monitored the rate of drug overdose deaths and acute care utilization (e.g., emergency room visit) in Massachusetts.

The study recruitment was held in 351 communities in Massachusetts between 2006 and 2009. Nineteen communities, which reported five or more drug overdose deaths annually between 2004 and 2006, were targeted to initiate interventions for drug overdose. Study participants were opioid users (defined as current use or at recovery stage) who were at risk for drug overdose and their bystanders. The investigators provided education on drug overdose and on management of drug overdoses to patients who were opioid users and their bystanders. The education was a modified version of the Harm Reduction Coalition and the Chicago Recovery Alliance, and participants learned current circumstances of drug abuse, risk reduction of drug overdose deaths, emergency rescue breathing, and administration of intranasal naloxone. The rescue kits were distributed to all study participants. The naloxone rescue kits were dispensed to 2,912 people. The kits were used in 327 times, and opioid users used 286 unique individuals (87.5%).

Overall, naloxone was effective in improving unresponsiveness and respiratory depression. The success rate was 98% (opioid users: 98%; bystanders: 100%), and one or two doses of naloxone did rescue patients with unresponsiveness and respiratory depression. Among all study participants who used the naloxone rescue kit, 95% used it for someone other than themselves, such as friends, partner or family, or strangers. Among opioid users, only 6% used the rescue kit for themselves. Among bystanders, 43% used the rescue kit for friends, 41% for partners or family, and 16% for strangers.

The results of this study illustrate that availability of the naloxone rescue kits saved not only people at risk of opioid overdose death but also their friends, family members, or strangers whose risk of opioid overdose death was unidentified. Additionally, the higher the study enrollment rate, the more effective the rescue kit was in preventing drug overdose deaths.

• Similar studies with naloxone in New Mexico (studies in Taos, Roswell, and Santa Fe)¹⁵

In New Mexico, the NMDOH conducted a similar pilot study with naloxone for the prevention of drug overdose deaths in the Taos, Roswell, and Santa Fe areas. The pilot study started in January 2013, and the investigators monitored the following items at enrollment to determine which risk factors a study candidate had for drug overdose deaths among opioids and other illicit drug users, such as history of substance abuse, diagnosis of psychiatric diseases, concurrent liver, kidney, and/or respiratory disease(s), high daily dose of opioids.

The investigators also assessed reasons for the use of a naloxone rescue kit (overdose, outdated, lost, stolen, or destroyed); who the kit was used for (person who is prescribed opioid or not); other medications (heroin, cocaine, benzodiazepine, alcohol, "meth"); utilization of healthcare providers/institutions; and utilization of emergency call.

The NMDOH reported that the investigators in three areas have continued recruitment of study candidates.

Innovation of Proposed Study

Currently, a significant amount of attention is being directed to the use of COT. Given

that New Mexico ranks third in the United States for the rate of accidental overdose deaths associated with prescribed opioid use, this attention is warranted. Prescribing intramuscular and intranasal naloxone rescue kits to high risk patients receiving chronic opioids to treat chronic pain has been employed recently as one effort that might decrease the accidental overdose rate associated with these medications. In past studies, risk stratification criteria have been employed to select patients on chronic opioid therapy who may benefit most from the use of an intramuscular or intranasal naloxone rescue kit. This method could inadvertently exclude patients who also may benefit from this therapy. Patients who do not fit the current definition of high risk criteria, such as anyone on chronic opioid therapy with comorbid dementia who forgets they already have taken their opioid mediation and the takes a second dose, or a patient whose metabolism of an opioid is changing, still may be at risk for adverse events associated with chronic opioid therapy. Rather than using inclusion criteria to select patients who receive naloxone auto-injector, a model that does not define "high risk" patients a priori, may offer improved benefits from the use of naloxone auto-injector. If a "universal precautions" method is employed, much in the same manner as epinephrine injection dispensed to patients with a history of anaphylaxis, or a glucagon pen and/or glucose tablets being dispensed to patients who use insulin to treat diabetes, the prescribing of naloxone auto-injector to all patients on chronic opioid therapy for chronic pain may have a greater impact on the accidental overdose morbidity/mortality rate associated with the use of chronic opioid therapy. Additionally, it may be beneficial to make naloxone available as a universal precaution for people who were not prescribed opioid to decrease mortality due to drug overdose. According to previous naloxone studies, a significant amount of opioid mortality occurs among those for who the opioid wasn't prescribed.^{11,12}

Year 1- ASAP Study

Since April 2016, we have enrolled 358 patients at ASAP in our prospective nonrandomized clinical trial using the Evzio autoinjector. We have documented 82 overdose reversals thus far. Only one of the reported overdose reversals was from the study patients at ASAP, while the other 81 overdose reversals were from community members received naloxone from the study patients. For every 100 patients enrolled in the study, approximately 23 overdose reversals have been reported. We have submitted a peer-reviewed article about this data, and are now waiting to hear back regarding acceptance of the submission.

3. Study Design

- 3.1. The previous study at ASAP is a prospective observational study using the naloxone 0.4 mg auto-injector which took place April 4th, 2016 through April 30th, 2017.
- 3.2. Evaluation of patients enrolled include: # overdoses reversed, # naloxone doses needed, urine toxicology, history of overdoses witnessed, history of being reversed by naloxone, demographic information, medical history, etc.
- 3.3. For this current study, we propose the following new additional studies:
 - A biostatistical logistic regression analysis to study the characteristics of the study subjects who performed the overdose reversals (vs. the study subjects who did not).

8 | [Type text]

- A qualitative study to examine in-depth the characteristics of study subjects who a) documented many overdosed reversals/"saved" many community members, b) documented one overdose reversal/"saved" one community member, and c) did not document any overdose reversals
- Study the 2 mg Evzio autoinjector product to prospectively analyze the difference in doses (2 mg vs. 0.4 mg) needed to reverse an overdose. The goal will be to recruit 100 patients in one year and document between 20-30 overdose reversals in the community.

4. Inclusion and Exclusion Criteria

Inclusion Criteria

- A. All patients treated with naltrexone, methadone or buprenorphine as medication assisted treatment at the UNM Addiction and Substance Abuse Program (UNM ASAP) aged 18 or older.
 - Over 70% of patients at UNM ASAP on medication assisted treatment use methadone
- B. Subjects who sign a consent form.

Exclusion Criteria

- A. Subjects who are allergic to naloxone and its inactive ingredients.
 - Inactive ingredients: buffering agents
- B. Subject younger than 18.

5. Number of Subjects

The University of New Mexico Addiction and Substance Abuse Program (UNM ASAP) will be the research site, to include all subjects with a DSM-V diagnosis of substance use disorder. The UNM ASAP treats approximately 600 patients for substance use disorders with diagnosis of opioid dependence disorder annually. Ninety percent of these patients are treated daily as a part of their federally funded methadone maintenance treatment program. The remainder are treated with buprenorphine or naltrexone as opioid replacement therapy. Naltrexone has an FDA indication to treat opioid dependence.

We will explain the study to all potential candidates; however, 20-30% of the patients may decline to participate in the study.

We are enrolling study subjects at a current rate of approximately 6-10 subjects per month and anticipate this continuing throughout the year. Additionally, we can anticipate that our current study population is reporting a steady overdose reversal rate of 23% for every 100 patients enrolled. This number has not changed since July 2016.

Power analysis: the occurrence of opioid overdose death at the UNM ASAP is approximately 10% annually. With a sample size of 500 people we will have 80% power to detect a 20% difference in mortality at alpha level of 0.05.

6. Study Timelines

The research team submitted the initial IRB application at the beginning of October 2015. Recruitment at UNM ASAP will start in January 2016, after receiving IRB approval. The research team will follow the study subjects for one year and will close the study when qualitative interviews have been completed.

If the IIS is approved, the research team will begin the logistic regression analysis as soon as possible. Once the IRB approves the qualitative modifications, the face-to-face 1:1 interviews will begin with the study subjects.

The recruitment for the Second Year Study will begin June 1, 2017 at UNM ASAP, after receiving IRB approval for protocol amendment. The research team will follow a study subject for one year and will close the study when qualitative interviews have been completed.

7. Study Endpoints

There are four endpoints in this study:

- 1. Number of fatal over dose deaths and near fatal overdoses averted by use of naloxone auto-injector co-prescribing from the University of New Mexico Addiction and Substance Abuse Program (UNM ASAP)
- 2. To study the characteristics of the study subjects who performed the overdose reversals (vs. the study subjects who did not) using a logistic regression analysis
- 3. To qualitatively study the in-depth characteristics of study subjects who a) documented many overdosed reversals/"saved" many community members, b) documented one overdose reversal/"saved" one community member, and c) did not document any overdose reversals
- 4. Study the 2 mg Evzio autoinjector product to prospectively analyze the difference in doses (2 mg vs. 0.4 mg) needed to reverse an overdose. The goal will be to recruit 100 patients in one year and document between 20-30 overdose reversals in the community. (Between April 4th 2016 and April 4th 2017, 383 study subjects were enrolled and there were 93 reported overdose reversals)We are currently enrolling new patients at the rate of 6-10 new patients per month.

8. Research Setting

Research facility: The study is conducted at UNM ASAP.

UNM's ASAP is a part of the behavioral health program under the UNM Psychiatric Center. ASAP specializes in providing diverse, proven substance abuse and mental health treatment, including specialized services for women. ASAP provides services to adults and adolescents with a primary substance abuse diagnosis and/or individuals who have a substance abuse disorder along with other mental health issues. Location: [name]

9. Resources Available

Study personnel Principal investigator:

[name] MD, professor, Department of Neurosurgery, School of Medicine As medical director and founder of the UNM Pain Center and ECHO Pain clinic at the

10 | [Type text]

University of New Mexico, [name] has played key roles in improving access to specialty care for chronic pain patients, as well as in improving the quality of care by providing consultative, educational, and therapeutic services to patients throughout New Mexico. She has a broad background in neurology, pain and headache management, neurorehabilitation, and traumatic brain injury, and for the past three years she has effectively led the interdisciplinary team of pain specialist at Project ECHO. She will serve as an investigator on this project. This proposed project is a collaboration study with the New Mexico Department of Health and will definitely reduce drug overdose deaths, which are a serious public health issue in New Mexico.

Co-investigators (alphabetical order)

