[name], [name] and [name] will be responsible for data storage and will share the data with other IRB-approved investigators on an as needed basis. [name] and [name] may share the data with a biostatistician at the Clinical Translational Science Center for the purpose of data analysis. The biostatistician will follow HIPAA regulations and keep the data in accordance with the data storage policy at CTSC.

17.Data and Specimen Banking

In accordance with the IRB at the UNM Health Science Center (UNM HSC), the investigators commit that the data will be used only for the research purpose and not to identify individual study subjects. The investigators will use minimum identifiers (e.g., date of birth, last clinic visit) to protect the identity of the participants.

18. Risks to Subjects

The research team assumes the following risks during the study: adverse reactions from naloxone and loss of confidentiality.

1. Adverse reactions from naloxone

Reported adverse reactions from naloxone for opioid overdose were tremor and hyperventilation associated with an abrupt return to consciousness.¹⁶ According to the package insert, the abrupt reversal was described as follows: "Abrupt reversal of opioid effects in persons who were physically dependent on opioids has precipitated signs and symptoms of opioid withdrawal including: body aches, fever, sweating, runny nose, sneezing, piloerection, yawning, weakness, shivering or trembling, nervousness, restlessness or irritability, diarrhea, nausea or vomiting, abdominal cramps, increased blood pressure, tachycardia." The frequency of these adverse reactions is unknown. These adverse reactions are not life-threatening, and hyperventilation will be managed

18 [Type text]

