Because naloxone is an antidote of opioids and only minor adverse reactions were reported in the similar clinical studies, the investigators will not anticipate serious adverse reactions. The research team will encourage all study subjects to report any adverse reactions from naloxone at each visit, if a subject uses the rescue kit. The research team will examine the causality and severity of the adverse reaction with the Naranjo algorithm and Common Terminology Criteria for Adverse Events (CTCAE) v4.0. If a serious adverse reaction occurs and the reaction is related to naloxone, the study team will compensate the patient for the cost of an emergency room visit and necessary patient's care (primary care physician's visit, medications, etc.).

25.Consent Process

The research team will obtain consent from all study subjects. The consent process will take place at the ASAP. The research team will provide enough time for a potential study candidate to understand the clinical study and to ask any study-related questions of the research team and study coordinator until all concerns are resolved. The research team also will explain that participation in the study will not affect the quality of a subject's primary care, whether or not the subject agrees with the participation. As described in Section 24 in this protocol, healthcare providers at the ASAP will identify potential study candidates. The candidates will be asked if they are interested in taking part in the study. Then the candidate will be referred to an investigator on the team. The investigator will explain the clinical study and answer questions, such as about risks and benefits, from the study candidates. After the candidate understands the study and agrees to sign the informed consent form (ICF), the candidate becomes a study subject and will receive naloxone rescue kits. The research team will follow "SOP: Informed Consent Process for Research (HRP-090)."

Non-English Speaking Subjects

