We do recruit Native Americans but this research is not intended to target American Indian/Native populations nor is it conducted on tribal lands. While participants may be of these populations we are not seeking out these participants. We have a wealth of experience with persons of tribal descent and therefore we are sensitive to the local population in terms of tribal regulations, applicable laws and standards of professional conduct and practice.

32.Transnational Research

Not applicable

33.Drugs or Devices

Drug²³

- Generic name: Naloxone hydrochloride injection, USP
- Brand name: EVZIO

22 | [Type text]

- Strength: 0.4 mg/0.4 mL in each kit²¹ and 2 mg/0.4 mL in each kit²²
- NDC number
 - o 0.4 mg kit: 60842-030-01²¹
 - 2 mg kit: 60842-051-01²²
- Manufacturer: Kaleo
 - Richmond, VA 23219
- Pharmacology²⁴
 - Naloxone is an antidote of opioids and has been used frequently for patients whose condition is opioid intoxication or for patients with respiratory depression with therapeutic opioid doses. Several formulations are available: intravenous, intramuscular, and subcutaneous injections are commonly used administration routes. However, adverse events due to opioid overdose can occur at any time. Thus, a convenient drug formulation of naloxone is necessary to administer naloxone to prevent drug overdose deaths, regardless of a patient's knowledge.
- Pharmacokinetics
 - Time to peak: 15 minutes
 - Maximum serum concentration 1.24 ng/mL
 - Time to maximum concentration: 20 minutes
 - Metabolism:
 - Primarily metabolism route: liver via glucuronidation
 - Elimination half-life: 1.36 hours
 - Excretion: Urine (as metabolites)
- Indications²⁴
 - Emergency treatment of known or suspected opioid overdose, as manifested by respiratory and/or central nervous system depression.
 - Immediate administration as emergency therapy in settings where opioids may be present.
- Necessity of Investigational New Drug (IND) application
 - No. This product has an FDA approval in 2014.
- Drug storage
 - Naloxone auto-injector is stored at 15-25°C (59-77°F).²¹ Access to the naloxone auto-injector should be limited to the investigators at UNM ASAP.
 - The naloxone auto-injectors are stored in a secure area in the medication room in UNM ASAP. A pharmacist at UNM Investigational Pharmacy will maintain logs to track who the naloxone autoinjectors are dispensed for regulatory requirements (Appendix 7 and 8).¹⁷
- Drug destruction

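### Endpoint 4 compares 2 mg with 0.4 mg on doses needed alone; no comparison of withdrawal or other reactions by strength is planned

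*Combined protocol and SAP*

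**What the plan says.** Sections 1, 3.3 and 7 describe the dose comparison in the same terms: the 2 mg product is to be studied "to prospectively analyze the difference in doses (2 mg vs. 0.4 mg) needed to reverse an overdose". The target is also the same: "The goal will be to recruit 100 patients in one year and document between 20-30 overdose reversals in the community". The 0.4 mg data come from the earlier cohort, which Section 3.1 calls a prospective observational study. Sections 1 and 7 report 93 reversals among 383 subjects for it.

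On harm, Section 18 quotes the package insert: "Abrupt reversal of opioid effects in persons who were physically dependent on opioids has precipitated signs and symptoms of opioid withdrawal". It adds that how often this happens is not known and that these reactions do not threaten life.

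On collection, Section 14 says study subjects will be asked about withdrawal symptoms at clinic visits. Section 24 encourages study subjects who use a kit to report reactions, and says the team will "examine the causality and severity of the adverse reaction with the Naranjo algorithm" and CTCAE v4.0.

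For each reported overdose, the Section 12 interview covers when naloxone was given and at what dose, the clinical outcome (reversal, death, health-care use), who received it, the opioid involved and whether 911 was called. It lists no reaction or withdrawal item. Section 13 names neither a reaction variable nor a grouping by strength.

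**The concern.** A comparison of two strengths normally sets what the larger one may gain against what it may cost. The protocol names a possible cost, withdrawal on abrupt reversal, but the strength comparison has no outcome that measures it. If fewer injectors were used per reversal at 2 mg, a reader would have nothing from the same study to weigh against that result. Conversely, if recipients of 2 mg had more reactions, no planned table would show it.

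The gap begins at data collection. The reaction questions are worded for study subjects, but the people given naloxone are almost always someone else. Grading done well on study subjects alone would leave the recipients' experience largely unrecorded.

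**Working it through.** **1. Where a comparison of reactions by strength could sit**

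- Section 7, endpoints: no reaction outcome.
- Section 12, per-reversal interview: dose and clinical outcome, but no reaction item.
- Section 13, analysis: no reaction variable and no strength grouping.
- Section 14, safety board: quarterly and unscheduled meetings, with no display by strength.
- Section 16, outcome parameters: kits dispensed, reason, circumstances, reversals and prescription data, but no reaction item.
- Sections 14 and 24: withdrawal questions and grading, worded for study subjects and not by strength.

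**2. The plan's own figure**

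The strength ratio is 2/0.4 = 5. Section 2 gives 82 reversals in 358 subjects, and Sections 1 and 7 give 93 in 383. Per 100 enrolled, 100 × 82/358 = 22.9 and 100 × 93/383 = 24.3. Both lie inside the target of 20 to 30, so that target reproduces.

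**3. How many reactions the study-subject wording would reach**

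Section 2 attributes 1 of 82 reversals to a study patient and 81 to community members; 1/82 = 1.2%. If the same share held at 2 mg, the expected number of reversals in study subjects would be 20 × 1/82 = 0.24 to 30 × 1/82 = 0.37.

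**4. What a table by strength could show**

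The best case is recipient data on all 93 reversals at 0.4 mg and on m = 20 to 30 at 2 mg.

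*No events at 2 mg.* The one-sided 95% upper limit is 1 − 0.05^(1/m): 13.9% for m = 20 and 9.5% for m = 30.

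*Interval width.* If the rate is 10% at both strengths (assumed), the 95% half-width for the difference is 1.96 × √[0.1 × 0.9 × (1/93 + 1/m)]: 14.5 percentage points for m = 20 and 12.3 for m = 30.

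*Power.* The documents give no reaction rate, so a range is assumed. The method is a two-sided 0.05 test of two proportions with a pooled null variance. Power = Φ{[|p₂ − p₁| − 1.96 × √(p̄(1 − p̄)(1/93 + 1/m))] / √(p₁(1 − p₁)/93 + p₂(1 − p₂)/m)}.

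For 10% against 20% with m = 20, p̄ = (9.3 + 4)/113 = 0.118. The two standard errors are 0.0794 and 0.0947, so Φ[(0.1 − 0.1557)/0.0947] = Φ(−0.59) = 28%. With m = 30 it is 33%.

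| Assumed rate at 0.4 mg | Power to detect a doubling (m = 20 to 30) | Rate at 2 mg detectable with 80% power (m = 30 to 20) |
|---|---|---|
| 5% | 18% to 20% | 24.0% to 27.5% |
| 10% | 28% to 33% | 32.6% to 36.6% |
| 20% | 48% to 59% | 46.6% to 51.1% |
| 30% | 72% to 84% | 58.5% to 63.1% |

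**5. The dose-count side, same method**

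If the share of reversals needing more than one injector fell from an assumed 30% to 10%, power would be 44% to 62%. For a fall from 20% to 10% it would be 14% to 21%. Doses needed is not a strong basis for a conclusion either.

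**The case against.** The strongest reply is that this is a pilot, that safety is not ignored, and that the real gap is broader. Section 12 records the naloxone dose alongside death, EMS, emergency-room and hospital use, so serious consequences could be related to dose. Sections 14 and 24 provide for withdrawal questions, formal grading and a board that meets at once after an unexpected reaction. The protocol regards the known reactions as not life-threatening. Section 13 names no analysis by strength for any outcome, including doses needed, so the missing reaction comparison may reflect an unfinished plan for endpoint 4 and not a one-sided choice. The data forms (Appendices 3 and 4) are not in the supplied text and may hold a reaction field. The Section 24 wording could also be stretched to reactions in someone on whom a subject used the kit.

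Much of this stands. It limits the point to a gap in the endpoint, the listed interview items and the analysis; it does not show neglect of safety. But health-care use does not measure withdrawal, and nothing in the text brings reactions into the strength comparison.

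A reader might infer two stronger claims that the documents do not support:

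- *The outcome can only favour 2 mg.* The plan does not say whether doses means injectors or milligrams. In milligrams, one 2 mg injection exceeds two at 0.4 mg (2 × 0.4 = 0.8 mg), so the result could favour 0.4 mg. The 0.4 mg cohort is earlier and non-randomised, so differences between cohorts could move the count either way.
- *A higher reaction rate at 2 mg would be diluted by pooling with 0.4 mg data.* No section says safety data are pooled across strengths. Section 3.1 ends the 0.4 mg study on April 30, 2017, and Section 6 starts second-year recruitment on June 1, 2017. The text only omits to say that strengths will be shown separately.

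**Conclusion.** The point holds as a gap in the comparison. Endpoint 4 sets two strengths, five-fold apart, against each other on doses needed alone. No reaction comparison is planned, and the collection wording would reach about 0.2 to 0.4 expected reversals in study subjects out of 20 to 30. That last figure assumes the earlier 1-in-82 share carries over and that the unseen forms have no recipient item. If they have one, only the endpoint, analysis and board display need changing.

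The protocol nowhere says it will prefer one strength; the risk lies in how a dose-count result would be read. Adding reactions would not settle the trade-off. At these numbers only large differences are detectable, and the figures assume independent reversals with complete data, although objective 3 expects some subjects to report many. The gain is that harms are visible by strength and the conclusion is limited accordingly. This is a worthwhile, inexpensive improvement, and it takes no view on which strength is right.

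**What to change.** - **Section 12:** add to the existing per-reversal interview the recipient's withdrawal or other reaction as reported, the injector strength and the number of injectors used.
- **Endpoint 4 and Section 13:** add a descriptive table, by strength, of the proportion of reversals with a reported reaction and its CTCAE grade, with confidence intervals and no hypothesis test. Show reversals with unknown reaction status separately, and do not count them as free of reactions.
- **Section 14:** show the same table by strength at the three-monthly board meetings.
- **Interpretation:** state that no preference between strengths will be concluded from dose count alone, because the 0.4 mg cohort is earlier and non-randomised.

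The cost is an amended form, one table and two sentences, with no new visit, procedure or staff. The drawbacks are that reports on recipients will be second-hand and harder to grade, the earlier 0.4 mg reversals may have no recipient reaction data to compare with, and the intervals will be wide.
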